2.4 DNA and RNA Sequencing

Sequencing for this study will be performed at Ashion Analytics, LLC (Ashion). Ashion is a CLIA-certified laboratory developed by TGen in order to perform whole exome and RNA sequencing in a clinical laboratory to ensure the accuracy, reliability, and quality of the data. The sequencing will be performed on the Illumina HiSeq 2500 Sequencer. Quality thresholds will include metrics such as base calling quality, coverage, allelic read percentages, strand bias, and alignment quality. Once data has passed all QC thresholds, the de-identified data will be preprocessed and uploaded directly to the NMTRC TransMed software for creation of the NMTRC Drug Prediction Report.

Data Flow

At enrollment in the study, a patient record will be created and the tumor and blood samples for the patient will be given a sample identifier and stored in the NMTRC laboratory management database (LIMS). The samples, tagged with the LIMS sample identifier, will then be sent to the CLIA laboratory in Phoenix, AZ. Once there, whole exome sequencing and RNA sequencing will be performed on the tumor sample. Whole exome sequencing will also be performed on a blood sample from the patient. For exome sequencing, fastq files are aligned with BWA 0.6.2 to GRCh37.62 and the SAM output are converted to a sorted BAM file using samtools 0.1.18. BAM files are subjected to indel realignment, mark duplicates, and recalibration steps in this order with GATK 2.2 where dpsnp135 is used for known SNPs and 1000 Genomes’

ALL.wgs.low_coverage_vqsr.20101123 is used for known indels. Lane level sample BAMs are then merged with Picard 1.79 if they are sequenced across multiple lanes. Variant calling is done with Unified Genotyper and the output VCF files are recalibrated with VariantRecalibrator from GATK 2.2. SnpEff 3.0, and SnpSift 1.7 is then used to annotate these VCF files with database version GRCh37.66. For RNA sequencing, lane level fastq files are appended together if they are across multiple lanes. These fastq files are then aligned with TopHat 2.0.6 to GRCh37.62 using ensembl.63.genes.gtf as GTF file and the resulting BAM files are assembled with Cufflinks 2.0.2 using the same GTF file and ensembl.63.genes.MASK.gtf as the mask file. HTSeq 0.5.3 is used to count the number of reads spanning each gene. Changes in transcript expression are calculated with Cuffdiff 2.0.2. For novel fusion discovery, reads were trimmed to 50 base pairs and then aligned with TopHat-Fusion 2.0.6. At the completion of RNA Sequencing, two files will be produced that will be consumed by the personalized medicine reporting engine. The first of these files is a VCF file that specifies the variants that were observed in the tumor sample. The second file is an FPKM file that specifies the expression levels of genes in the tumor sample. Both of these files will be in the VCF 4.1 format - an example of the VCF 4.1 format for expression is shown in the appendix. At the completion of the whole exome sequencing, a single file VCF file containing the variants for the tumor sample and identifying them as either somatic or germ line by comparison to the normal blood sequence. The tumor variants will be in VCF4.1 spec generated by Seurat 2.5. An example of a variant (for the V600E mutation of BRAF) is shown in the appendix below where AR is allele ratio, DP1 is depth of normal, DP2 is depth of tumor, LN1 is length. The effect of the variant is extracted with the following regular expressions, regex is $EFF=\w((.*))\w/$.

Patient data captured on the Ashion server is encrypted and pushed via a file transfer server (FTP) for secure delivery of data to authorized NMTRC study personnel. The LIMS system contains a file detection system that will identify when samples are made available on the FTP site. These files, tagged with the sample identifiers will be pulled from the FTP site and imported into the LIMS system. The LIMS system will then process the three files into a personalized medicine report as described in the algorithms section.

2.5 NMTRC Drug prediction report

The following describes the NMTRC report generation which utilizes data generated from Ashion (as described in section 2.4 above).

Predicted Therapeutic Compounds: At this time, there are currently greater than 200 drugs within the NMTRC drug library each with previously defined or inferred molecular targets. For the purposes of this protocol, the tumor board will only use the drugs listed in Appendix III.

Algorithms

There will be three drug matching algorithms utilized in this molecularly guided therapy protocol.

1. Direct variant/drug matching
2. Inferred variant/drug matching
3. Expression of biomarkers/drug targets (biomarker expression)

The algorithms are described in detail below. Although there will not be formal ranking of the drug calls, there are different levels of confidence in the three algorithms and as such, the drugs will be listed in the report in the order of the confidence in the algorithms that identified them as candidate therapies for the patient (Direct variant first, followed by inferred variants, followed by biomarker expression). This is because sequence variants (whether direct or inferred) provide stronger evidence of tumor dependence than simple gene expression calls, with direct drug/variant relationships being the highest confidence of all three. Within the biomarker expression, the drugs will be listed in descending order from most to least differentially expressed.

Variant drug matching

The NMTRC LIMS system has a database that contains a table linking drugs, variants, and genes with evidence from peer reviewed literature. The patient's tumor variants from the VCF files produced by Ashion are linked to the variants and genes in this table to identify potential therapies. This matching provides the output for direct variant/drug matching and inferred variant drug/matching. The inferred and direct refer to the strength of the evidence supporting the relationship between the drug and the variant. The first level of confidence, direct evidence indicates that the literature indicates that 1) the variant has been directly associated with a change in response to the therapy (either becoming more sensitive or more resistant) and the gene is the target of the drug or 2) the variant has been directly shown to activate the pathway for which the drug is a target or 3) the variant has been associated with changes in response to the drug due to indirect mechanism including but not limited to transportation or metabolism. Evidence of direct activation of the drug target by the variant is considered a sensitivity indicator, unless there is specific evidence that the variant induces resistance to the drug. The second level of confidence,

inferred evidence, indicates that the variant is in a gene that is a direct target of a drug and is computationally predicted to have biological impact in the gene, but the variant has not been directly associated with changes in response to drug or activation of target. For inferred variants the variant must be a somatic mutation (present in the tumor only) and also have a minor allele frequency from the 1000 genomes project which is less than 0.5%. Whether the evidence is direct or inferred will be indicated by a column in the report. The evidence that resulted in the drug selection will be provided as a hyperlink in the table.

Biomarker Expression

The third algorithm utilizes the gene expression as measured by RNASeq. A consistent step for the NMTRC methodologies outlined in this proposal is the conversion of normalized probe set intensities to a relative measure of transcript abundance. We utilize a standardized z-score method (described below in Signal Pre-Preprocessing and Z-Score Calculation) to determine statistically significant differences in each sample relative to a whole body reference and relative to cancer reference. This method assigns a z-score to each probe set based upon the number of standard deviations from the normal sample population mean. This provides a good assessment of transcript “differences” relative to a whole body reference or cancer reference sets which may not necessarily be associated with large fold changes in transcript expression. Having established a consistent data input of relative transcript abundance in each subject’s tumor specimen, the following analytical methods will be applied to the standardized data to predict drug efficacy.

The method is fundamentally very straightforward. There are two classes of expression rules. The first of these rules are biomarker rules and are of the type “overexpression of gene g1 implies sensitivity (or insensitivity) to drug d1” or “underexpression of gene g2 implies sensitivity (or insensitivity) to drug d2” whereas the second is “g3 is the target of drug d3, thus overexpression of g3 implies sensitivity to d3”. The NMTRC LIMS contains a database of drugs and the genes along with a column that implies whether over or under expression of that gene indicates sensitivity (or insensitivity) to the drug and the evidence for that rule. In order for a gene to be called over or underexpressed a method is required to identify calls. This is described in more detail in the next section.

Gene expression calls

Two distinct perspectives are consistent with using over- or underexpression to guide therapy but suggest different sets of reference samples and different statistical tests. If gene expression level is interpreted to reflect sensitivity of a cell to a drug then elevated (alternatively, depressed) expression should be *anomalous* by comparison with normal cells throughout the body (the whole body normal reference). The drug should then kill the tumor cells before it kills normal cells. We call elevated (depressed) expression relative to samples of the whole body Normal Reference using a standard score (Z-score), referred to as the NRZ.

In contrast, if gene expression level in a cancer cell is interpreted as reflecting comparative drug sensitivity among cancer cells then elevated expression should be called based on its *rank* among other cancer samples (the cancer reference). We call elevated (alternatively, depressed) expression relative to the Cancer Reference based on the Cumulative distribution, referred to as the CRC statistic.

We report indications based on both the NRZ and CRC, based on only the NRZ, and based on only the CRC. For each such indication we report both the NRZ and the CRC.

Normal Reference Z-score (NRZ)

$$NRZ = \frac{X_q - \bar{X}_R}{s_R}$$

where X is the normalized expression of Anders and coworkers [43]. q indicates the query (cancer) sample, \bar{X}_R is the reference sample mean of X , and s_R is the reference sample standard deviation of X . The NRZ is consistent with the statistic we used previously for microarray-based expression measurements. We use a threshold of 2, that is, $NRZ > 2$ indicates overexpression $NRZ < -2$ indicates underexpression. The normal reference set comprises 42 normal tissues, organized into 21 tissue types: Adrenal Gland, Brain, Bronchus, Corpus uteri, Corpus Uteri, Esophagus, Gland, Heart, Large Intestine, Liver, Lymph Node, Nipple, Prostate Gland, Salivary Gland, Skeletal Muscle, Skin, Small Intestine, Spleen, Testis, Tonsil, Uterus. Many (28) of the samples are also given a sub-type designation, for example, Brain: Hippocampus.

Cancer Reference Cumulative statistic (CRC)

$$CRC = \begin{cases} E_{i \in C}[Z_i > 2] & \text{Overexpression} \\ E_{i \in C}[Z_i < -2] & \text{Underexpression} \end{cases}$$

where $E_{i \in C}[\cdot]$ indicates an average over the set, C , of cancer *cases*, $Z_i = \frac{X_q - \bar{X}_i}{s_C}$ is the standard score for the query by comparison with cancer case i , \bar{X}_i is the mean associated with samples from case i , and s_C is the sample standard deviation, obtained from C . CRC estimates the proportion of cancer samples that are less extreme than the query, that is, a higher CRC indicates more strongly for treatment based on the rule. For example, with an overexpression rule, $CRC = 1$ means that expression in the query sample was higher than in all cancer reference samples by at least 2 standard deviations. We have chosen to call samples that are in the top quartile ($CRC > 0.75$) as elevated or depressed in expression. We also identify genes support by both NRZ and CRC when $NRZ > 2$ and $CRC > 0.5$.

In contrast to the use of the use of the NRZ, with which the objective is to call anomalous expression, comparison with the cancer reference requires estimating the quantile associated with X_q . The proportion of cancer samples that express a gene at a level below the query sample might be estimated using the empirical cumulative distribution function, for example, in the case of overexpression

$$E_{i \in C}[X_q > X_i].$$

However, variation arises as a result of biological differences between tumors and as a result of differences in observations of the same tumor. If all tumors were biologically identical with respect to expression of a gene then quantiles would reflect exclusively the observation and variation would not be relevant. Since our cancer reference set includes samples representing pediatric oncology tumors we can estimate the variation *within* cancer case and therefore estimate the proportion of cancer cases for which expression of the gene falls significantly below (overexpression) or above (underexpression) the query.

Report:

The process of report generation begins when all of the sequencing data is available on the FTP server. If gene matches gene in the database then aberration is checked. For each gene/variant that

matches a rule in the rules database, a row will be generated in the report. All variants supported by direct evidence will be listed first in the report indicating their greater clinical significance and an indication that the relationship is supported by direct evidence. If an aberration meets the criteria for an inferred indicator of drug response (described in the algorithms section) it will generate a line in the report which indicates that the relationship between the drug and gene is inferred. For each differentially expressed biomarker indicating/not indicating, a line will be generated in the report. For all rows in the report there will be a link to the PubMed article that supports the identified aberration/drug relationship. The set of rules will be in a read only database that will be inaccessible for changes during the trial.

The software has been validated to show that:

1. 100% reproducible output given the same input.
2. Simple yet sophisticated rules management.
3. Cross reference data with several open source data sets.
4. Generation of a clinically understandable, actionable report.

Positive mutation findings from the whole exome and RNA sequencing will be verified using Sanger Sequencing. While all attempts will be made to have this data available to the tumor board, due to the potential length of time to process Sanger Sequencing samples, these results may not be available until after the tumor board has met and the patient has started protocol treatment. If Sanger Sequencing results differ from the original sequencing, the results and the subject has already started protocol treatment, this information will be communicated to the treating site Principal Investigator who will then communicate this information to the patient and a mutual decision about continued treatment will be made.

3 Treatment Protocol Decision

3.1 Decision Making Rules for Treatment Regimens

Treatments protocols will be generated from the molecular tumor board meeting utilizing the information contained in a report generated on the basis of genomic analysis of the gene expression profile of the subject's tumor. The molecular tumor board consists of pediatric oncologists, pharmacists, bioinformations, genomicists, and pathologists (as available). Specific treatment details will consist of a regimen chosen from a guided list of agents implicated in critical molecular signaling pathways summarized in the guided therapy reports and may include one standard chemotherapy agent not included on the report. All agents are listed in the current FDA approved pharmacopoeia with age appropriate dosing, but will differ amongst individual subjects.

3.1.1 Decision rules for the committee will include:

1. All drugs with predicted efficacy will be reported to the tumor board. At this time, FDA approved and over the counter medications predicted by one of the different predictive methodologies under evaluation will be included. For these panels the analytical methods are independently applied to the standardized and normalized (relative to whole body and cancer reference sets) gene sequencing data derived from the profiling of each subject's tumor. Each method is associated with an objective statistical threshold that must be

exceeded in order for a specific drug to be predicted and reported for consideration. Molecular-based predictions of drug efficacy will be supplemented with evidence gathered from searching of the literature, clinical trials and the internet.

2. Drugs must be FDA approved or available over the counter with established standard and safe age appropriate dosing schedules.
3. Potential drug choices will be analyzed with regards to safety, mechanism, availability and cost. Focus will be on low-toxicity, targeted therapies.
4. Drug combinations will be allowed, up to a maximum of 4 agents. Literature searches will be conducted to assemble data on previously established and tested regimens. These regimens will be given priority.
5. A pharmacist will analyze potential drug interactions between the guided agents and the subject's routine medications and supplements. For drug interactions and known toxicities the following databases will be used: MicroMedex LexiComp, Facts and Comparisons, Natural Medicines Database.

Subjects' history and previously received treatments will be reviewed. Drugs which a subject has failed will be given low priority and used only if there is a rationale for synergy in combination therapy.

3.1.2 Recommended priorities for determining drug dosing to be used in individualized treatment plans include the following:

1. For a given proposed individualized combination of drugs the first priority to establish doses will be to identify the same combination of drugs in a peer-reviewed journal article or presented as a reviewed abstract, or which is part of an ongoing peer-reviewed clinical trial registered with clinical trials.gov.
2. When a proposed individualized combination of drugs has not previously been reported, the process to establish doses will be to then identify individual members of the proposed combination that have been used in combination with other cytotoxic agents similar to those being considered for combination therapy. The source of information will be a peer-reviewed journal article or presented as a reviewed abstract, or which is part of an ongoing peer-reviewed clinical trial registered with clinical trials.gov.
3. When a proposed individualized combination of drugs have no available combination data, dosing guidelines will start with the MTD determined from a phase I/II pediatric study. Reference information will be based upon either a peer-reviewed journal article or presented as a reviewed abstract, or which is part of an ongoing peer-reviewed clinical trial registered with clinical trials.gov. Doses will be reduced to compensate for potential additive toxicities of combination agents.

Please note that many of the drugs that will be considered for proposed individualized combination therapy in this protocol are not considered cytotoxic agents and therefore will not have previously been specifically tested as part of conventional antineoplastic protocols. Examples of these medications may include anti-seizure or anti-cholesterol agents. These non-cytotoxic agents will be used at standard doses based on recommendations of an experienced pediatric pharmacist and described pharmacy programs that are used to evaluate potential interactions and combination dosing for all medications. The final treatment regimen will be subjected to a 12 hour in depth review and evaluation for safety and then be signed off by one of the protocol pharmacists. The treatment memo will then be discussed with the subject and their parents (if the subject is < 18 years of age).

3.2 Additional Biopsies:

Subjects that are having additional biopsies done as standard of care during the course of the study, when deemed appropriate by study PI, may complete the study process again and have new reports generated on the latest tumor. A new tumor board discussion will occur utilizing all rules of this protocol and the new reports. The subject may then change treatment regimens based on the decision of the tumor board. All protocol requirements and specifications will be followed as if it were a new biopsy.

3.3 Safety Evaluations

The principal investigator and the study chairs will evaluate reported serious adverse events and other toxicities in real time. Study chair and PI meetings will occur at least monthly. The principal investigator will meet with the clinical research team at frequent and regularly scheduled intervals to determine treatment modifications and treatment based toxicities.

Any safety concern or new information that might affect either the safety or the ethical conduct of this trial will be immediately forwarded to the study chairs in written form. The NMTRC will be responsible for informing the central IRB and DSMB. If trends in toxicities are noted or stopping rules are met, the study chair will temporarily suspend enrollment while reviewing the episodes with the DSMB. The DSMB will convene every 6 months for evaluation of all safety data.

Study will be on hold for safety monitoring by DSMB review when:

1. Any deaths deemed related to the study drug by the treating PI while on study or occurring less than 30 days after medications ended or 2 serious adverse events possibly related to protocol within 60 days.
2. Any other reason that the NMTRC feels it is in the best safety interest of the subjects.

Subjects will be required to either come off study or be dose reduced per treating physician standard of care if one of the following toxicities related to treatment regimen occurs. Toxicity will be graded according to the NCI-Common Terminology Criteria for Adverse Events (CTCAE v4.0).

Non-Hematologic toxicity:

- ≥Grade 3 non-hematological toxicity not resolved to <Grade 2 or baseline within 2 weeks excluding nausea, vomiting, anorexia, hypertension, electrolyte abnormalities corrected with oral supplementation.

Hematologic toxicity:

- Grade 4 neutropenia lasting ≥14 days;
- Grade 4 neutropenia with Grade 4 infection

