While individual biomarkers may be predictive of responses to specific therapies, especially in the context of front-line treatment, a different approach to the management of patients with refractory disease is needed in order to identify effective treatments from the catalog of available agents. Advances in informatics and molecular technologies, coupled with our expanding knowledge of molecular networks and mechanism of action of the existing pharmacopeia, provide a great opportunity in translational medicine to develop a model that more accurately predicts tumor response. The studies outlined in this proposal are a step in the development of personalized oncology, in which each patient is truly treated individually based upon the systematic molecular analysis of their disease. Our project is focused on testing the merits of a specific data-driven predictive method through which any number of drugs in our current knowledge base has a chance of being recommended, of these only the FDA approved drugs listed in Appendix III will be used. Although this novel approach to personalized therapeutics brings with it the concern that toxicities that may arise from novel combinations of agents, it is strongly felt by the investigators that the logical interpretation of molecular data by a committee of highly qualified physicians and pharmacists in order to identify drug candidates for consideration in the treatment of a patient population with few alternative options is a worthwhile endeavor. The systematic biomarker-driven approach outlined in this proposal, by tailoring a combination of drugs targeting the specific molecular composition of a tumor—irrespective of tumor classification or anatomical origin—provides a feasible alternative to the conventional approach that targets specific organs or tissues without consideration of the underlying tumor biology.

A Pilot Trial Testing the Feasibility of using Molecular-Guided Therapy in Patients with Refractory or Recurrent Neuroblastoma.

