10.1.2 Unexpected Adverse Event

An **unexpected adverse event** is one for which the nature or severity of the event is not consistent with the applicable product information as outlined in package insert filed with the FDA.

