10.1.5 Expedited Reporting of Serious Adverse Events

All fatal or life-threatening adverse events must be reported to the NMTRC immediately by telephone, fax, or e-mail within 24 hours of knowledge of the event. If full information is not known, additional follow-up by the Investigator will be required.

All other serious adverse events that are related and unexpected (not listed in the relevant appendices) which occur any time after the subject has been consented up to 30 days after the last dose of treatment, and are possibly, probably, or definitely related to the research must be reported to the study chair and appropriate regulatory authorities (local IRB and FDA if required) within 7 days of notification of the event.

The Investigator must report all serious adverse events reported to regulatory authorities in an expedited manner to the local IRB or IEC. All serious adverse events must be followed until resolution or stabilization. Unanticipated problems involving risk to subjects or others, serious adverse events related to participation in the study, and all volunteer deaths related to participation in the study should be promptly reported to the NMTRC.

NMTRC Reporting Contact

Please report all expedited reports to:

[name] and [name]
NMTRC
[contact]
E-Mail: [contact]
E-Mail: [contact]

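### The study-hold rule counts every possibly related SAE, but the only day-limited duty for non-life-threatening SAEs and the adverse event form leave out expected ones, so the 60-day count can be late or incomplete

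*Combined protocol and SAP*

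**What the plan says.** Section 3.3 holds the study for DSMB review after any death attributed to study drug, on study or within 30 days of stopping, or after "2 serious adverse events possibly related to protocol within 60 days". It also allows the NMTRC to call a hold at its discretion. The second trigger does not mention expectedness.

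Section 10.1.5 sets out how SAEs reach the coordinating group:

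- Fatal or life-threatening events: "All fatal or life-threatening adverse events must be reported to the NMTRC immediately by telephone, fax, or e-mail within 24 hours". No relatedness or expectedness condition applies.
- Remaining SAEs: "All other serious adverse events that are related and unexpected (not listed in the relevant appendices") go to the study chair and to regulatory authorities ("local IRB and FDA if required) within 7 days of notification of the event").
- A later sentence, addressed to the NMTRC, covers related SAEs without an expectedness condition and without a time limit: "serious adverse events related to participation in the study, and all volunteer deaths related to participation in the study should be promptly reported".

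Section 10.1.2 calls an event unexpected when its nature or severity is "not consistent with the applicable product information as outlined in package insert filed with the FDA". Section 10.1.6.2 places the attribution category 'possible' under related.

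Section 10.1.4 keeps all adverse events in source documents, but requires the adverse event form only for events of at least Grade 3 that are both related and unexpected. Section 12.2 gives the DSMB summaries drawn from the database. Section 3.3 has the DSMB meet every 6 months.

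**The concern.** A rule that counts events in a fixed window works only if every event it counts arrives within a known time. Here the counting rule and the timed reporting rule cover different sets of events. SAEs that are possibly related, labelled, and neither fatal nor life-threatening are in the first set and not in the second.

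This is the trial's only numeric pause based on SAE counts, in children receiving individualised combinations of up to 4 agents. Section 1.2 itself raises "the concern that toxicities that may arise from novel combinations of agents". If qualifying events arrive late, enrolment can continue after the plan's own condition for a hold has been met. Six months is about three 60-day windows, so the scheduled DSMB meeting is a slow backstop. It may also be an incomplete one if the summaries are built from the adverse event form.

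**Working it through.** The documents state no operating characteristic for the hold rule and no expected SAE rate, so there is no figure to reproduce. The check is a comparison of texts.

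**Step 1. Which rule covers which event**

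| SAE, at least possibly related | Counts toward hold (3.3) | Reporting time (10.1.5) | Adverse event form (10.1.4) |
|---|---|---|---|
| Fatal or life-threatening, unexpected | Yes | 24 hours, to NMTRC | Required |
| Fatal or life-threatening, expected | Yes | 24 hours, to NMTRC | Not required |
| Other, unexpected | Yes | 7 days, to study chair and authorities | Required if Grade 3 or above |
| Other, expected | Yes | Promptly, to NMTRC; no number of days | Not required |

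The last row is the gap in timing. The second and last rows show the gap in the form.

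**Step 2. Whether another route closes it**

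- The instruction to report promptly does reach the last row, because 'possible' is classed as related. It gives no number of days.
- The real-time review in 3.3 is of SAEs already reported, so it depends on the same inputs.
- Section 3.3 requires safety concerns to be forwarded to the study chairs immediately, but does not name SAEs. A site may not regard a labelled toxicity as a concern.
- Study chair and PI meetings are at least monthly (3.3), and sites hold a monthly teleconference (9.6). About two of each fall in 60 days. Neither section assigns the 60-day count to anyone.

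**Step 3. Worst-case illustration**

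Two inputs are assumed and are not in the documents: λ, the expected number of possibly related SAEs that are neither fatal nor life-threatening in one 60-day window, and u, the share of them that is unexpected. I also assume that no expected event arrives through the undated route. With Poisson counts,

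P(at least 2 events) = 1 − e^(−m)(1 + m),

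where m = λ if all events are counted and m = λu if only unexpected ones arrive.

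| λ | All counted | u = 0.75 | u = 0.50 | u = 0.25 |
|---|---|---|---|---|
| 1 | 0.264 | 0.173 | 0.090 | 0.026 |
| 2 | 0.594 | 0.442 | 0.264 | 0.090 |
| 4 | 0.908 | 0.801 | 0.594 | 0.264 |

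For example, with λ = 2: 1 − e^(−2) × 3 = 0.594. With u = 0.50, m = 1 and 1 − e^(−1) × 2 = 0.264.

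Conditional on exactly 2 such SAEs having occurred, so that a hold is due, both fall under the 7-day duty with probability u². This is 25% for u = 0.50, 6% for u = 0.25 and 1% for u = 0.10. With 4 such SAEs, the chance that at least 2 do is 69%, 26% and 5% (binomial, n = 4).

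These figures show direction and the outer range only. They ignore an instruction that the protocol does contain.

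**The case against.** The strongest reply is that 10.1.5 already covers these events. The sentence on prompt reporting has no expectedness condition, 10.1.6.2 counts 'possible' as related, and the recipient, the NMTRC, informs the DSMB and can call a hold itself. The protocol uses 'should' loosely (10.1.4 uses both 'should' and 'must' for capturing events), so the sentence need not be read as optional. Monthly meetings add further chances to notice a cluster. All of this stands. What remains is that the duty has no deadline, the form filter excludes the events, and no one is named to keep the count.

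Four stronger readings are tempting, and the documents do not support them.

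- A reader might infer that labelled SAEs need never be reported. A site that never reported one would be departing from 10.1.5, not following it.
- A reader might infer that 10.1.5 contradicts itself. The 7-day sentence and the prompt-reporting sentence differ in scope and recipient, and a site can follow both.
- A reader might infer that a toxicity on the label of any one agent is automatically expected for the whole combination. Section 10.1.2 does not say so, and it tests severity as well as nature, so a labelled toxicity that is worse in combination can still be unexpected.
- A reader might note that Appendix III lists only drug names, so that under the appendix wording in 10.1.5 nothing is expected. That reading would bring every related SAE under the 7-day duty and remove the timing gap. Section 6 refers to Appendix III for known side effects drawn from package inserts and databases, which suggests that broadly the same source was meant. This is a reason to reconcile the two references, not a separate defect in the hold rule.

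**Conclusion.** The point holds as a mismatch between a counting rule and its inputs. Labelled, possibly related SAEs that are neither fatal nor life-threatening count toward the hold in 3.3, but they have no numeric reporting deadline in 10.1.5 and no required place on the adverse event form in 10.1.4. The 60-day count can therefore lag or be incomplete. The DSMB's summaries can be incomplete too, on the assumption that they are built from that form.

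The size cannot be derived from the documents. The probabilities shown are a worst case under assumed rates and should not be quoted as the chance of a missed hold. The conclusion rests on the text alone, reading expectedness by the package-insert definition in 10.1.2. It is worth correcting because it concerns the trial's only numeric SAE trigger and the remedy uses a time limit that the protocol already has.

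**What to change.** - In 10.1.5, require every SAE that is at least possibly related, expected or not, to reach the NMTRC and the study chair within the existing 7 days. Keep the 24-hour limit for fatal or life-threatening events as it is.
- In 10.1.4, require all such SAEs to be recorded in the database, so that the DSMB summaries under 12.2 contain them.
- In 3.3, name the NMTRC as keeper of the running 60-day count. The threshold itself does not change.
- Keep the expectedness filter only for onward reporting to the FDA and IRB, and reconcile its two references: the package insert in 10.1.2 and the appendices in 10.1.5.

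The cost is a revised paragraph in 10.1.5, matching lines in 3.3 and 10.1.4, a form change and a memo to sites. Sites will send somewhat more SAE reports, and holds may be more frequent, which is what 3.3 already calls for.
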